the LR and TACE candidates were determined following the BCLC and HKCL guidelines. Among the patients who underwent LR therapy (Supplement 6A-C), the PTA model identified 1386 potential LR candidates, BCLC guidelines selected 1196 cases, and HKCL chose 1765 candidate patients. K-M cures clearly showed that the survival difference between recommended and non-recommended populations was the largest in the PTA model compared with other guidelines. Meanwhile, the hazard ratio (HR) calculated by Cox regression analysis was 10.6, 2.02, and 1.93 respectively in the PTA model, BCLC, and HKCL guidelines (non-recommended as reference). Likewise, among the patients who accepted TACE, the PTA model, BCLC, and HKCL guidelines discriminated 323, 964, and 521 cases, respectively. The HR for the PTA model, BCLC, and HKCL guidelines was 25.4, 0.901, and 0.503, respectively (Supplement 6D-F).

Moreover, the LR candidates recommended by the PTA model had a prolonged OS compared to those suggested by BCLC and HKLC (Figure 2A); a similar conclusion was reached for the TACE group (Figure 2B). Intriguingly, the PTA model also found potential allocation “error” populations in the TACE and LR groups, depicted as hypothetical K-M curves (Figure 3A-B). The MST predicted by the PTA model was significantly higher compared with that of the original therapy allocation, suggesting that alternative therapies can enable patients to achieve a better prognosis and that mistaken allocation either to LR or TACE is still abundant. The patients with actual treatment and LR or TACE candidates are clearly shown in Figure 3C. Regarding the original LR allocation, 1458 cases had the right allocation, while 458 “model-found” cases were misled and should have been given TACE therapy. Similarly, there were abundant erroneous allocations among the original TACE allocations (2752, 89.5%).

Given that BCLC, the HKLC staging system, and PS could affect the prognosis of the potential benefit-gained population, we stratified patients into different BCLC subgroups (BCLC 0-A, BCLC B, and BCLC C stages; Supplement 7), HKLC subgroups (HKLC I-II and HKLC III; Supplement 8), and different PS (PS0 and PS1; Supplement 9). The PTA model could accurately select benefit-gained patients for LR

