and TACE across different BCLC and HKLC stages and PS. Collectively, the K-M curves and HR consistently showed that the PTA algorithm could more effectively select TACE and LR candidates than the two authoritative therapeutic guidelines.

Web development and clinical application

To make an easy-to-apply tool and visualize the individual predictive results, we implemented the PTA models as a web interface, which could be freely accessed from www.pta4hcc.com. Users may input four groups of parameters: (a) demographic information, such as age and gender; (b) liver function; (c) tumor burden files; and (d) routine laboratory results like kidney function. The PTA model calculates the survival rate for each month when adopting different treatments (now including LR and TACE) and generates MST, all of which can be displayed on the user-friendly interface. For example, a 65-year-old man with hepatitis B virus infection and no prior treatment would possess a better prognosis if LR therapy was adopted instead of TACE after the diagnosis of HCC. His tumor burden characteristics are as follows: the number of tumors is four, the maximum tumor size is 8 cm, the AFP is 300 µg/L, and the ECOG or PS is 0. In addition, the information on the other two groups is also input into the website in the complete version. The output is his predicted survival curves derived from the PTA model, showing that LR's MST is 78 months, while TACE's MST is only 23 months (Supplement 10).

In parallel with the complete PTA algorithm, a concise version including the nine most important features was also developed on this website. This simple AI version could also calculate the integrated survival model immediately upon the input of these important features, especially for cases where some above-stated module features were unavailable. For example, a patient with two tumor lesions, a tumor size of 12 cm, 100 µg/L AFP, good PS, 120 g/L HGB, 35 U/L AST, 40 g/L ALB, and normal INR would benefit from TACE therapy rather than LR. The simulative survival curve indicates that the MST was 15 and 10 months for TACE and LR allocation, respectively (Supplement 11).

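### The comparison of PTA with BCLC and HKLC pools the whole cohort, about 84% of it PTA's own training patients, so PTA's survival separation and hazard ratios (10.6 and 25.4) are mostly in-sample while the guidelines' are not

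*Combined protocol and SAP*

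**What the plan says.** Section 3 (Model development) describes K-fold cross-validation with a grid search for tuning, after which the component models are refitted in the training set. Section 4 (Model estimation) defines a candidate by comparing the median survival times that PTA predicts under LR and under TACE. It takes the BCLC and HKLC candidate definitions as given.

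The Results section on basic clinical characteristics gives a training set of 1622 LR and 2570 TACE patients and a validation set of 294 LR and 505 TACE patients.

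The section on comparison with clinical guidelines then reports, without naming a cohort:

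- For LR-treated patients: "Among the patients who underwent LR therapy (Supplement 6A-C), the PTA model identified 1386 potential LR candidates". BCLC selected 1196, and "HKCL chose 1765 candidate patients".
- The LR hazard ratio "was 10.6, 2.02, and 1.93 respectively in the PTA model, BCLC, and HKCL guidelines (non-recommended as reference").
- For TACE-treated patients, 323, 964 and 521 candidates for PTA, BCLC and HKLC. "The HR for the PTA model, BCLC, and HKCL guidelines was 25.4, 0.901, and 0.503, respectively".
- On survival, "the LR candidates recommended by the PTA model had a prolonged OS compared to those suggested by BCLC and HKLC".
- On reallocation: "Regarding the original LR allocation, 1458 cases had the right allocation, while 458" were judged better suited to TACE. "Similarly, there were abundant erroneous allocations among the original TACE allocations (2752, 89.5"%).

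From the Kaplan–Meier curves and hazard ratios together, the section concludes that "the PTA algorithm could more effectively select TACE and LR candidates than the two authoritative therapeutic guidelines".

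**The concern.** A fitted model is being compared with two fixed rules largely on the patients used to fit the model. For a training patient, the predicted survival under the treatment received was learned partly from that patient's own outcome. The candidate label depends on that prediction, and the label is then tested against the same outcome. A flexible model can call a long TACE survivor a TACE candidate partly because that patient survived. BCLC and HKLC cannot gain in this way, so any optimism is one-sided.

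At stake is the claim closest to treatment allocation: that PTA picks LR and TACE candidates better than two established guidelines. The text gives no validation-only version of that claim, and the model is offered on a public website. The reported misallocation counts (458 LR and 2752 TACE) come from the same mostly in-sample predictions, although the direction of any bias in those counts is undetermined.

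Two reporting problems make the comparison harder to read. With non-recommended patients as reference, hazard ratios of 10.6 and 25.4 would mean that recommended patients die faster, against the text's statement of prolonged survival. In the TACE arm, PTA's hazard ratio (25.4) and the guidelines' (0.901 and 0.503) lie on opposite sides of 1.

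**Working it through.** **1. Reproduce the stated split.** 4192/4991 = 84.0%, as printed. By arm, 1622 + 294 = 1916 LR and 2570 + 505 = 3075 TACE.

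**2. Find which cohort can hold the reported counts.**

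| Count | Validation arm | Training arm | Implication |
|---|---|---|---|
| LR: PTA 1386, BCLC 1196 | 294 | 1622 | too many for validation |
| LR: HKLC 1765 | 294 | 1622 | too many for either set alone |
| LR: 1458 + 458 = 1916 | – | – | full LR arm |
| TACE: BCLC 964, HKLC 521 | 505 | 2570 | too many for validation |
| TACE: 2752 | 505 | 2570 | too many for either set alone |
| TACE: 323 + 2752 = 3075 | – | – | full TACE arm; 2752/3075 = 89.5%, as printed |

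**3. Training share.** LR 1622/1916 = 84.7%; TACE 2570/3075 = 83.6%. At least 1386 − 294 = 1092 of PTA's LR candidates (78.8%) are training patients. So are at least 2752 − 505 = 2247 of the TACE patients it does not recommend (81.6%).

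**4. Evidence that optimism exists.** In the section on selection of the optimal AI model, PTA's C-index falls from 0.854 in training to 0.801 in validation. The random survival forest, one of PTA's six components, falls from 0.926 to 0.765, which the text itself reads as potential over-fitting. These falls do not convert to the hazard-ratio scale without patient data.

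**5. LR counts.** 1386 + 458 = 1844, which is 72 short of 1916. The 1386 candidates and the 1458 rightly allocated patients therefore also differ by 72, unexplained.

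**6. What a validation-only analysis could deliver.** If the whole-cohort shares hold, PTA would recommend 294 × 1386/1916 = 213 of 294 LR patients, leaving 81. Using 1458 instead gives 224 and 70. In TACE it would recommend 505 × 323/3075 = 53 of 505.

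For precision, assume proportional hazards, longer survival in recommended patients, the published hazard ratios and complete follow-up. Let p be the recommended share and S the recommended group's survival. Solve p·S + (1 − p)·S^HR = arm survival. Then SE(log HR) = √(1/d₁ + 1/d₂), where d₁ and d₂ are deaths in the two groups, and the 95% factor is exp(1.96·SE).

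| Setting | Arm survival, 3 and 5 years | Recommended deaths | 95% factor each way |
|---|---|---|---|
| TACE validation, HR 25.4 | 41.5%, 26.4% | 2.1 to 3.4 | 3.8 to 2.9 |
| TACE all 3075, HR 25.4 | same | 13 to 21 | 1.7 to 1.5 |
| TACE validation, HR 5 (assumed) | same | 10 to 14 | 1.9 to 1.7 |
| LR validation, HR 10.6, p = 1386/1916 | 79.6%, 70.8% | 15 to 26 | 1.8 to 1.6 |

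On the same assumptions, a hazard ratio of 25.4 implies about 96% three-year survival in recommended TACE patients, against 79.6% in the whole LR arm. That does not prove optimism, but so extreme a value needs an out-of-sample check.

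**The case against.** The strongest reply has four parts.

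- **The in-sample reading is an inference.** The text does not say whether these predictions came from fold-wise or final fits, and the details sit in Supplement 1 and the code repository, neither of which was available. This stands as a caveat. However, refitting in the training set is what is described, out-of-fold prediction is not, and the gaps between training and validation C-indices look like apparent fitting.

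- **Another comparison with the guidelines is probably held-out.** The section on predictive performance compares PTA with BCLC and HKLC by C-index and AUC. Its confidence intervals fit the validation set by the Hanley–McNeil approximation, ignoring censoring. The LR three-year AUC has a reported SE of (0.903 − 0.797)/3.92 = 0.027, against 0.032 expected with 294 patients and 0.013 with 1916. The TACE one-year AUC has 0.018, against 0.020 with 505 and 0.008 with 3075. This is real support for PTA's prognostic ranking. It does not test the candidate classification, the survival curves or the hazard ratios, on which the selection claim rests.

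- **The measured optimism is modest and may not change the ranking.** This stands: the size of the lead is unreliable, but the ranking is not shown to be wrong.

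- **The hazard-ratio direction and the count mismatch are separate defects.** They are, and would exist with perfect predictions. The reference-group note is attached only to the LR sentence, so carrying it over to TACE is itself an inference. These defects are not what makes the main point serious, but they must be settled before the comparison can be read.

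**Conclusion.** The concern holds and should be corrected before the selection claim is relied on. The counts leave no reading but the full arms, so 84.7% of the LR comparison and 83.6% of the TACE comparison are PTA training patients. The two guidelines carry no matching advantage. On the narrative's reading that recommended patients live longer, the bias favours PTA, and hazard ratios of 10.6 and 25.4 cannot be taken as its performance in new patients.

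This rests on two assumptions: that the predictions for training patients came from models fitted to those patients, which is what the text describes, and that the guideline rules were applied as published. The size of the inflation is unknown, and PTA may still outperform both guidelines out of sample. The precision figures are illustrative and best-case. They assume complete follow-up, whereas median TACE follow-up is 36.1 months, and they use the very hazard ratios in doubt.

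**What to change.** 1. Rebuild the candidate classification, Kaplan–Meier curves, hazard ratios with 95% confidence intervals and Figures 2–3 on out-of-fold predictions for the 4192 training patients, with tuning and the ensemble refitted inside each fold, plus held-out predictions for the 799 validation patients.
2. Report the validation-only result alongside. Note that it is imprecise for TACE, and that the validation C-index was also used to prefer PTA over the single algorithms, so it is not wholly untouched.
3. Label the present figures as apparent performance and name the cohort.
4. State one hazard-ratio reference group and use it for both arms and all three rules.
5. Reconcile the 1386 LR candidates with the 1458 called rightly allocated.

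The cost is extra model refitting in each fold and probably less favourable hazard ratios. The pooled out-of-fold analysis evaluates the modelling procedure rather than the single model on the website, so the validation-only result is needed as the check on that model. It is workable for LR and weak for TACE, where about 53 patients would be recommended, with only 2 to 3 deaths if a hazard ratio of 25.4 held. Items 3 to 5 need no refitting.

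### The claim that PTA selects LR and TACE candidates better than BCLC and HKLC rests on same-treatment contrasts in mostly training patients, and the LR hazard-ratio label and candidate counts do not reconcile

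*Combined protocol and SAP*

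**What the plan says.** Section 4 (Model estimation) defines an ideal LR candidate by a gain of more than 50% in predicted median survival time (MST) over the primary treatment, and an ideal TACE candidate by a gain of more than 50% over LR.

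The Results section Comparison with clinical guidelines applies this in each arm:

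- **LR-treated patients.** "the PTA model identified 1386 potential LR candidates", against 1196 for BCLC and 1765 for HKLC. The HR "was 10.6, 2.02, and 1.93 respectively in the PTA model, BCLC, and HKCL guidelines (non-recommended as reference").
- **TACE-treated patients.** The candidate counts are 323, 964 and 521. "The HR for the PTA model, BCLC, and HKCL guidelines was 25.4, 0.901, and 0.503, respectively", with no reference group restated.
- **Kaplan-Meier curves.** "K-M cures clearly showed that the survival difference between recommended and non-recommended populations was the largest in the PTA model".
- **Candidates compared across systems.** "the LR candidates recommended by the PTA model had a prolonged OS compared to those suggested by BCLC and HKLC", and "a similar conclusion was reached for the TACE group (Figure 2B").
- **Misallocation.** Patients said to be wrongly allocated are "depicted as hypothetical K-M curves (Figure 3A-B"). In the LR arm 1458 allocations are called right and 458 wrong; in the TACE arm 2752 (89.5%) are called wrong.

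The section ends by stating that "the K-M curves and HR consistently showed that the PTA algorithm could more effectively select TACE and LR candidates" than the two guidelines.

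**The concern.** Choosing between LR and TACE needs evidence on how outcomes differ between the treatments for a given type of patient. The HRs and the recommended-versus-non-recommended curves compare patients who all had the same treatment. One such HR can be large because the rule separates good from poor prognosis, whatever the other treatment would have done. The section opens by calling the exercise a comparison of discriminative performance, which these results can address. Its conclusion goes further.

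Three further points add to this:

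- The HRs appear to come from the pooled cohort, so PTA is judged largely on data it was fitted to.
- As printed, the LR reference group makes PTA candidates die faster, against the prose.
- Error in allocation is inferred from the same predicted MST that defines a candidate.

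The model is offered on a public website that shows an MST for each treatment. Readers could take prognostic separation as evidence on who benefits from which treatment.

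**Working it through.** **1. Counts.** Arm sizes are LR 1916 and TACE 3075 (Basic clinical characteristics).

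- LR: 1458 + 458 = 1916, which agrees. But 1386 + 458 = 1844, leaving 1916 − 1844 = 72 patients unexplained (equally, 1458 − 1386 = 72).
- TACE: 323 + 2752 = 3075 and 2752/3075 = 89.5%, which agrees. The errors are therefore everyone who is not a TACE candidate, including any patient below the 50% threshold in both directions.
- One reading of the 72 is that LR patients below the threshold count as right, while the same kind of TACE patient counts as an error. The text does not say.
- For an LR-treated patient the primary treatment is LR, so the LR definition taken literally compares LR with itself. How the 1386 qualified is not stated.

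**2. Cohort.** The training set has 1622 LR and 2570 TACE patients; validation has 294 and 505.

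- The 1765 HKLC candidates exceed both 294 and 1622, so the LR sets were pooled. The 1458/458 and 323/2752 splits fill both whole arms.
- Training shares: 1622/1916 = 84.7% and 2570/3075 = 83.6%. At least 1386 − 294 = 1092 (78.8%) of the PTA LR candidates are training patients.
- Selection of the optimal AI model reports possible over-fitting in one ensemble member, the random survival forest (C-index 0.926 falling to 0.765), and a fall for PTA from 0.854 to 0.801.

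**3. Direction of the HRs.** Let p be the candidate share of the arm, S the arm's printed survival and S0 the survival in the reference group. Under proportional hazards:

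- reference non-recommended: p·S0^HR + (1 − p)·S0 = S
- reference recommended: p·S0 + (1 − p)·S0^HR = S

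Inputs are S = 0.708 (LR, 5 years) and 0.748 (TACE, 1 year), with p = 1386, 1196 and 1765 of 1916, and 323, 964 and 521 of 3075. Implied survival of candidates:

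| | PTA | BCLC | HKLC |
|---|---|---|---|
| LR, 5 years, as labelled | 61.4% | 64.8% | 69.8% |
| LR, 5 years, reversed | 88.0% | 77.5% | 72.3% |
| TACE, 1 year, LR label carried over | 1.0% | 76.3% | 85.2% |
| TACE, 1 year, reversed | 98.7% | 73.2% | 60.6% |

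As labelled, PTA candidates live shortest, against the stated result. With 1458 in place of 1386 the PTA LR figure is 63.0% as labelled (still lowest) or 86.4% reversed. The reversed HRs (1/HR) are 0.094, 0.495 and 0.518 for LR, and 0.039, 1.11 and 1.99 for TACE. No single reference makes all three TACE HRs favour recommended patients.

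**4. What a within-arm HR can show.** As an illustration, a purely prognostic score with no treatment in the model was cut at the PTA shares (72.3% of LR, 10.5% of TACE). Non-recommended versus recommended HRs were 11.6 (LR-like) and 15.8 (TACE-like) at a C-index of 0.83, and 17.6 and 26.6 at 0.86. A single HR of the printed size therefore needs no ability to choose between treatments.

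**5. Can in-sample fitting produce an advantage in both arms?** Data were simulated with a constant LR-versus-TACE HR, so no interaction. Settings: n = 4991 with 4192 training; 10 covariates, 5 of them prognostic; log-hazard SD 1.5; prognosis-dependent assignment; survival forest alone or weighted with a proportional-hazards model; 4 replicates per setting. Patients were ranked by predicted LR/TACE MST ratio and cut at the printed shares. Whole-arm HRs (non-recommended versus recommended) were 1.7 to 8.4 in LR and 4.6 to 15.0 in TACE. In simulated validation patients they fell to 0.66–1.30 and 1.45–2.6. An advantage in both arms can thus appear without interaction. The simulation does not reach 10.6 and 25.4 together and does not estimate the bias in this study.

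**The case against.** The best counter-argument is that PTA-recommended patients, with the label reversed, do better in both arms. LR and TACE candidates lie at opposite ends of the predicted comparison, so one shared prognostic score would not explain this; it is an interaction at the level of association. That stands, and it is why step 4 bears on each HR singly and not on the pair. But no interaction test is described, the arms differ at baseline by the document's own account, and most patients were used for fitting. Confounding and in-sample fitting are not excluded.

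Other points:

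- **Unseen material.** Figures 2–3 and Supplements 6–9 are not available here and may hold confidence intervals, reference groups or further contrasts. The text does not state outright that Figure 2 is confined to treated patients. The finding is about the analyses as described.
- **Arm-specific discrimination.** Predictive performance of the PTA model gives AUCs of 0.893, 0.857 and 0.858 (TACE) and 0.873, 0.850 and 0.839 (LR) at 1, 3 and 5 years. The interval widths fit validation-sized samples. This supports prognosis within an arm; it does not validate the candidate cut or the choice of treatment.
- **The label.** It is probably one wrong parenthesis, since the prose gives the intended direction. The available text cannot confirm that.
- **TACE HRs.** The document never claims that guideline TACE candidates outlive non-candidates, so mixed directions are not in themselves a contradiction. The missing reference still has to be given.
- **Misallocation.** How many of the 2752 fall below the threshold in both directions is not reported, and could be few.

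**Conclusion.** The concern holds. The conclusion on candidate selection and the statement that misallocation is abundant go beyond the analyses described. Those analyses show within-arm prognostic separation, unadjusted as described, in a pooled cohort that is about 84% training patients. The only LR-versus-TACE contrast described is the model's own prediction.

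Separately, the printed LR reference reverses the order of the three systems (61.4/64.8/69.8% at 5 years, against 88.0/77.5/72.3% reversed), and 72 LR patients are unaccounted for.

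The count and cohort findings are plain arithmetic. The implied survival figures assume proportional hazards and the printed arm survival. The simulations show what is possible, not how large the bias is. This needs correction before the conclusion is relied on.

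**What to change.** 1. State or correct the HR reference in each arm, report all six HRs in one direction with 95% confidence intervals, and reconcile 1386 with 1458.
2. Call the within-arm HRs and curves prognostic separation, and report them for training and validation patients separately.
3. If the allocation claim is kept, compare LR-treated with TACE-treated patients inside the groups that PTA, BCLC and HKLC each assign to LR and to TACE. Adjust for the collected baseline variables, use out-of-fold predictions, and report a recommendation-by-treatment interaction. Otherwise limit the conclusion to prognosis.
4. Word the misallocation statements as model predictions, state the comparator in the candidate definition, and do not count patients below the 50% threshold as errors.

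**Cost.** Items 1, 2 and 4 need only re-tabulation and wording. Item 3 needs refitting within folds on data in hand, with fold models standing in for the deployed one.

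Its estimates will be less precise. The TACE-assigned group has 323 TACE-treated and 458 LR-treated patients, counts that refitting would change. Reversed-label survival implies about 323 × (1 − 0.960) = 13 TACE deaths by 3 years and 323 × (1 − 0.936) = 21 by 5 years. The LR deaths are about 458 × (1 − 0.452) = 251 and 458 × (1 − 0.258) = 340. The 95% confidence factor exp(1.96·√(1/d1 + 1/d0)) is then about 1.75 and 1.56. It is 1.9 to 2.2 if the effective sample halves, and 3 to 4 in validation patients alone. For the interaction ratio the corresponding factors are about 1.6 to 1.8, 1.9 to 2.3 and 3.2 to 4.4.

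The LR survival used here was solved for 530 non-candidates, not 458. Solving with 1458 candidates gives 0.212 and about 361 deaths at 5 years, which hardly changes the factor. Unmeasured confounding would remain and must be stated.

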Continuous and normally distributed variables were expressed as mean with a standard difference (SD) and compared using Student's t-test, while non-normally distributed variables were presented as median with interquartile range (IQR) and compared using the non-parametric Mann–Whitney U test. Categorical variables were expressed as numbers and percentages and tested by Fisher's exact test or the χ^2 test.

Overall survival (OS) was defined as the time interval between initial TACE or LR and all-cause death. Patients who survived up to the last follow-up date (October 15th, 2021) or were lost to follow-up were censored. Survival curves were displayed using the Kaplan–Meier (K-M) method and compared with the log-rank test.

Python software was applied for train AI models and detailed codes were uploaded as supplements (<https://github.com/ApocalypseZ/Survival>). R software and related packages (survival, rms, reportROC, survminer, and ggplot2) were adopted to conduct statistical analysis and plot figures. $P < 0.05$ was considered statistically significant.

Results information for studies

Basic clinical characteristics

In this multicenter study, 4991 patients met the selection criteria and were included. Of these, 1916 patients (38.39%) were amenable to LR while 3075 patients (61.61%) submitted to TACE (Figure 1). 4192 (84%) and 799 (16%) patients were divided into train and validation sets, respectively. Among train set, 1622 (38.7%) were underwent LR while 2570 (61.3%) adopted TACE treatment. In validation set, 294 (36.8%) and 505 (63.2%) were allocated to LR and TACE treatment, respectively. The demographic and clinicopathological characteristics of the cohort are shown in Table 1. The variables associated to tumor burden were lower in the LR group than those of the TACE group in overall cohort: (a) The largest tumor diameters were smaller in the

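### Figure 2A compares survival between overlapping candidate sets (at least 89.1% of PTA's LR candidates are also HKLC candidates), so an independent-groups test does not fit and the contrast does not show outcomes where the rules disagree

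*Combined protocol and SAP*

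**What the plan says.** Section 6 (Statistical analyses) gives one method for comparing survival curves: "Survival curves were displayed using the Kaplan–Meier (K-M) method and compared with the log-rank test". The statement is general and is not tied to any figure.

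The section Comparison with clinical guidelines applies each rule to the same patients. "Among the patients who underwent LR therapy (Supplement 6A-C"), it states that "the PTA model identified 1386 potential LR candidates, BCLC guidelines selected 1196 cases, and HKCL chose 1765 candidate patients" (HKCL is the document's variant spelling of HKLC). It first compares recommended with non-recommended patients within each rule, with hazard ratios of 10.6, 2.02 and 1.93 for PTA, BCLC and HKLC. It then compares the rules with each other: "the LR candidates recommended by the PTA model had a prolonged OS compared to those suggested by BCLC and HKLC" (Figure 2A), and says a similar conclusion holds for TACE (Figure 2B). The section closes by concluding, from the K-M curves and hazard ratios together, that PTA selects candidates more effectively than the two guidelines.

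The same section gives a second PTA count for the LR group: "1458 cases had the right allocation, while 458" were judged misallocated. Nothing in the document mentions overlap between the candidate sets, a cross-classification of the rules, or a method for dependent groups.

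**The concern.** Each rule is a yes/no label on the same LR-treated patients, so one patient can be a candidate under all three. Three curves drawn as if for three groups then contain many of the same people. Two things follow.

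First, a test for independent groups has the wrong variance, because a shared patient's outcome enters both sides and cancels in the difference.

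Second, the difference between whole candidate sets is not the difference between the rules where they disagree. HKLC selects 1765 of 1916 LR patients (92.1%), so its curve is close to that of the whole LR cohort. A smaller set that leaves out poor-prognosis patients can look better than HKLC even if the patients it adds do no better than those it drops.

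At stake is how far Figure 2A supports the conclusion that PTA outperforms two established guidelines. That conclusion is followed directly by a public web tool.

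**Working it through.** **Inputs**
- LR-treated patients: "Of these, 1916 patients (38.39%) were amenable to LR" (Basic clinical characteristics).
- Candidate counts 1386, 1196 and 1765 (Comparison with clinical guidelines).
- LR patients by cohort: "Among train set, 1622 (38.7%) were underwent LR"; the validation set has 294.

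**Denominator.** 1622 + 294 = 1916, and 1458 + 458 = 1916. The HKLC count of 1765 exceeds 1622, so the counts cannot come from the training set alone; they fit the whole LR group.

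**Minimum overlap.** For sets A and B within N patients, the overlap is at least |A| + |B| − N. The three sets total 1386 + 1196 + 1765 = 4347 against 1916 patients, so they cannot be disjoint.
- PTA and HKLC: 1386 + 1765 − 1916 = **1235**, which is 89.1% of PTA candidates and 70.0% of HKLC candidates.
- PTA and BCLC: 1386 + 1196 − 1916 = **666**, which is 48.1% of PTA candidates.
- With the other PTA count, HKLC: 1458 + 1765 − 1916 = 1307 (89.6%).

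The maximum overlaps are 1386 (PTA nested in HKLC) and 1196 (BCLC nested in PTA).

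**Discordant patients (PTA count 1386)**
- Against HKLC: 0 to 151 are PTA-only and 379 to 530 are HKLC-only.
- Against BCLC: 190 to 720 are PTA-only and 0 to 530 are BCLC-only.

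**Effect on the standard error.** With m shared patients and a common variance, the variance of a difference in means is proportional to 1/nA + 1/nB − 2m/(nA·nB). An independent-groups method omits the last term. The ratio of assumed to correct SE is the square root of (1/nA + 1/nB) / (1/nA + 1/nB − 2m/(nA·nB)).

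| Comparison | m | 1/nA + 1/nB | 2m/(nA·nB) | Assumed / correct SE |
|---|---|---|---|---|
| PTA vs HKLC | 1235 | 0.001288 | 0.001010 | 2.15 |
| PTA vs HKLC | 1386 | 0.001288 | 0.001133 | 2.88 |
| PTA vs BCLC | 666 | 0.001558 | 0.000804 | 1.44 |
| PTA vs BCLC | 1196 | 0.001558 | 0.001443 | 3.69 |

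At minimum overlap, a nominal 5% test has a true size of about 0.002% against HKLC and 0.5% against BCLC. A simulation of 4000 log-rank tests, with shared patients entered in both groups, agrees: the SD of z was 0.47 with no rejections (HKLC), and 0.69 with 0.6% rejections (BCLC). It used exponential survival at the reported LR 5-year figure of 70.8% and assumed uniform censoring at 20 to 90 months.

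**What the whole-set contrast measures.** Write survival at a fixed time as an average over cells (exact without censoring). At minimum overlap:
- PTA = (1235/1386)·S_both + (151/1386)·S_PTA-only
- HKLC = (1235/1765)·S_both + (530/1765)·S_HKLC-only
- Difference = 0.191·S_both + 0.109·S_PTA-only − 0.300·S_HKLC-only

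If PTA-only and HKLC-only patients had the same survival s, the difference would still be 0.191·(S_both − s). This favours PTA whenever shared patients live longer, although the discordant patients show no advantage for either rule. If PTA is nested in HKLC, the difference is (379/1765) = 0.215 times the contrast between shared and HKLC-only patients.

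Against BCLC, the smaller set, the corresponding coefficient is 666·(1/1386 − 1/1196) = −0.076. Set size would there work against PTA.

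**The case against.** **The error runs in the safe direction.** This stands. The independent-groups SE is too large, so the log-rank test is conservative under the null. A reader might infer that the overlap produced false significance; the arithmetic shows the opposite, and a correct SE would make any observed difference look more significant.

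**No log-rank P value is visible for Figure 2A.** This also stands. The figure is not shown, the sentence describing it gives no test, and Section 6 names the test only in general. The variance point is therefore conditional on that test being used. The point about the contrast needs no P value.

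**The superiority claim does not rest on Figure 2A alone.** Correct. The section leads with within-rule hazard ratios, whose groups do not overlap. Figure 2A is one part of the evidence.

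**Shared patients are not irrelevant.** Correct. The decomposition gives them net weight, and under nesting shared versus guideline-only is the informative contrast.

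**A purely discordant comparison may be unusable.** Also correct. The PTA-only cell against HKLC could be empty. Under proportional scaling it holds at most 151 × 294/1916 ≈ 23 of the LR validation patients, or about 23 × 0.292 ≈ 7 deaths by five years at the overall LR survival of 70.8%. That limits the remedy, but the present contrast remains hard to interpret.

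**Conclusion.** The point holds in a limited form. The printed counts force PTA and HKLC to share at least 1235 LR patients (89.1% of PTA candidates), and PTA and BCLC at least 666 (48.1%). The HKLC bound survives the discrepancy between the two PTA counts. A log-rank test of these sets would have an SE about 2.15 to 2.88 times too large against HKLC and 1.44 to 3.69 times against BCLC, so its P value is not valid and errs towards caution. The larger weakness is that the whole-set contrast mixes agreement and disagreement and cannot show which rule does better where they differ.

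This rests on three assumptions: Figure 2A uses the same LR-treated patients as Supplement 6A-C, which the adjacent text and the parallel wording for the TACE group support; the log-rank test was used, as Section 6 implies; and shared and unshared patients have equal variance, which is doubtful given a reported hazard ratio of 10.6. The last two affect only the SE figures.

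Two wider readings are not supported. The 89% figure does not extend to BCLC, where the forced overlap is 48.1%. Nor does forced overlap extend to Figure 2B: the TACE counts are 323, 964 and 521 of 3075, and 323 + 964 and 323 + 521 are both below 3075, so the minimum overlap with PTA is zero.

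**What to change.** For Figure 2A:

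1. Print the cross-tabulation of PTA against each guideline among LR-treated patients: both, PTA only, guideline only, neither. First reconcile the two PTA counts, 1386 and 1458. With 1458, the HKLC-only range changes from 379–530 to 307–458.
2. Replace any log-rank comparison of candidate sets with the difference in 5-year survival or restricted mean survival. Use a confidence interval from a bootstrap that resamples patients with all their rule labels, so that the overlap is kept. Report it overall and in the 294 LR validation patients, since 1622 of the 1916 were used for training.
3. Show K-M curves in the discordant cells descriptively where they are large enough. If one rule's set is nested in the other's, compare shared patients with those selected by the wider rule only.
4. State that the curves share patients, and by how many.

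For Figure 2B, print the same cross-tabulation and use the same bootstrap if the sets overlap.

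The cost is a few lines of code, a small table and one revised figure, with no new data. The drawback is wide intervals in the validation set and discordant cells that may be too small to interpret.
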